6.4.1 Objective

- Evaluate performance of qER

6.4.2 Outcome measures

- Sensitivity, specificity, positive and negative predictive values of qER in detecting scans with prioritized findings overall and also stratified by all 6 target abnormalities.
- AUC of qER in detecting presence of 6 target abnormalities

6.5 Health Economic Assessment

6.5.1 Summary

An economic evaluation will be conducted comparing costs and outcomes of a current provision of care in the NHS and one inclusive of qER. qER potentially impacts costs and benefits via two mechanisms: (1) the identification of critical findings can improve radiology reporting times; and (2) the identification of critical findings can support optimisation of patients clinical care, accelerating the treatment and referral pathways, and ultimately better outcomes.

The proposed health economic approach is a cost effectiveness analysis where both the clinical and financial impact of qER will be captured. This approach is chosen in accordance with the guidance in NICE's Evidence Standards Framework (ESF) for digital health interventions (reference). The ESF recommends the development of a cost effectiveness analysis to demonstrate the value of digital health interventions that are deemed to be higher financial risk. qER is categorised as a tier C intervention and is considered to be a high financial risk since the aim is to commission qER on large scale or potential nationwide adoption.

A cost utility model will be developed that allows extrapolation from clinical evaluation endpoints to estimates of incremental costs and quality adjusted life years (QALYs), comparing the use of qER with standard of care. It is likely the model will adopt a lifetime time horizon to capture the potential benefits qER may have on outcomes such as patient survival, surrogates of patient survival and/or long-term disability.

In order to capture such value components in the model, the model requires additional parameter estimates describing prognosis, and the relationship between 'time to treatment initiation' and treatment outcomes, to enable the extrapolation from the endpoints to overall survival (or a surrogate of overall survival), treatment costs and QALYs. The model will only include direct medical costs associated with qER and standard of care as well as implementation and maintenance costs necessary for the integration of qER as outlined in NICE's ESF.

The results of the model will include scenario and sensitivity analysis (both probabilistic and deterministic). These will be founded on alternative variations of parameter utilisation and care pathway design identified through engagement with the clinical advisory team during external validation. For example, a comparison of trusts with the presence of stroke centres and those not.

The following steps will be undertaken to develop the model:

A targeted literature review of previous published health economic studies evaluating head CT.

Using the findings from the evidence review, the appropriate model framework will be chosen for the cost utility model e.g., a Markov model, or decision tree. The model pathway will replicate the current standard of care and capture key therapy area characteristics. The identified model pathway will be tested with key opinion leaders (both clinical and economic).

A further evidence review will be completed to identify any required data that will not be collected in the prospective or retrospective clinical study e.g., health utilities.

A prototype of the economic model will be built in Microsoft Excel, incorporating the agreed data points with a focus upon key outputs of interest. The prototype will be completed in line with the interim results of the prospective and retrospective study to produce early cost effectiveness results. Updates to the model structure may be made to refine the economic value story.

A complete version of the economic model will be produced using results of the clinical trials. Results will be tested with clinical experts as well as an external health economist to the primary modelling team.

The results and version of the model will be documented along with a model quality assurance report.

Methods and results to be presented in a peer-reviewed manuscript suitable for submission to a peer reviewed journal.

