6.5.2 Objective

Compare costs and health benefits between pre and post implementation of qER and the associated ratios between the two to examine whether the ratio meets willingness to pay thresholds observed in England (i.e. £20,000 to £30,000 per QALY gained).

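### The protocol lets the economic model's structure be changed after early cost-effectiveness results are seen, gives no validity ground for a change, and does not require the pre-change result to be reported

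*Protocol*

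**What the plan says.** Protocol section 5.3 makes a cost-utility analysis of qER a secondary objective. Section 6.5.2 gives its yardstick: to examine "whether the ratio meets willingness to pay thresholds observed in England (i.e. £20,000 to £30,000 per QALY gained").

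Section 6.5.1 sets out how the model is to be built. On type, "the appropriate model framework will be chosen for the cost utility model e.g., a Markov model, or decision tree", guided by a literature review. On horizon, "It is likely the model will adopt a lifetime time horizon". Before any prototype exists, "The identified model pathway will be tested with key opinion leaders (both clinical and economic"). The section then describes how interim data are used: "The prototype will be completed in line with the interim results of the prospective and retrospective study to produce early cost effectiveness results". Directly after this comes a permission to alter the model, with its only stated purpose: "Updates to the model structure may be made to refine the economic value story". The final step follows once that permission has been given: "A complete version of the economic model will be produced using results of the clinical trials".

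The section also provides for scenario analyses, deterministic and probabilistic sensitivity analyses, a check of the results by clinical experts and an external health economist, a record of the model version with a quality assurance report, and a manuscript for peer review.

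**The concern.** A decision model that extrapolates from reporting time to lifetime QALYs depends heavily on structural choices: which states or branches exist, how long the horizon is, and how time to treatment is linked to survival and disability. If those choices can be revisited once a provisional cost per QALY is known, the final ratio may partly reflect which structure gave the more attractive answer. The usual protection is to fix a base case first and to allow departures only for reasons unrelated to the direction of the result. Here the protocol does not merely leave the point to a later plan. It grants the permission and states a purpose, and that purpose is neither model validity nor new evidence.

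What is at stake is the credibility of the cost-utility conclusion. Section 6.5.1 says that the aim is commissioning on a large, possibly national, scale. A reader could fairly discount a favourable ratio because of this one sentence.

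**Working it through.** No arithmetic applies. The protocol gives no cost, QALY, cost-effectiveness ratio or interim figure, so the check is one of sequence and of what each safeguard covers.

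**Step 1. Order of events in section 6.5.1.**

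| Step | Activity | Early cost-effectiveness result known? |
|---|---|---|
| 1 | Literature review | No |
| 2 | Framework chosen; pathway tested with experts | No |
| 3 | Further evidence review for missing inputs | No |
| 4 | Prototype completed with interim results | Produced here |
| 5 | Structure may be updated | Yes |
| 6 | Complete model built on trial results | Yes |
| 7 | Results tested by clinical experts and an external health economist | Yes |
| 8 | Version and quality assurance documented | Yes |

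The permission at step 5 falls after the first result and before the final model. The prototype sentence could be read as describing timing only, but its closing words, about producing early cost-effectiveness results, show that the interim data are used.

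**Step 2. How much is still open.** The framework is given only by example, and the horizon only as likely. Section 6.5.1 says that outside estimates are needed for prognosis and for the link between time to treatment and outcome. Section 6.5.3 takes utilities, and most costs other than those of the software, from published literature. There is real room for a structural choice to move the ratio.

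**Step 3. Does any safeguard close the gap?**

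- *Expert test of the pathway:* step 2, so it precedes the permitted change.
- *Sensitivity and scenario analyses:* described as varying parameters and care pathway design, with trusts with and without stroke centres as the example. Nothing calls for a comparison of the structure before and after a change.
- *External health economist:* examines results at step 7, after any change.
- *Documentation:* covers the results and the model version. No log of structural changes with reasons is required.

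Each helps, but none obliges the team to show what the ratio would have been under the structure that stood before the early results were seen.

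**Step 4. Is the point dealt with elsewhere?** Sections 15.1 and 15.2 describe neither an interim analysis nor any restriction on the economic model. No other section fixes the structure or limits the grounds for changing it.

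**The case against.** The strongest reply is that building a model in iterations is normal practice. A prototype exists to show where a structure fails, and the protocol says only that updates may be made. The verb is refine, not improve, and no change is conditional on an unfavourable result. The framework is to follow from an evidence review, and several independent checks are planned. A detailed specification of structure and horizon would ordinarily sit in a health economic analysis plan, which may exist. All of this stands, and it limits the point to an opportunity for bias; no bias is shown. It does not dispose of the point, because a later plan that froze the structure would contradict the permission written here.

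Several stronger readings are tempting but not supported:

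- *That interim comparative results will be released while sites are still switching, reach sites or the manufacturer, and be especially confounded with time.* The protocol neither dates the interim results nor says who receives them. Section 15.1 promises at least 3 months of post-intervention data at every site in a 12-month study, so all sites have switched by month 9 (12 − 3 = 9). A data cut after that could still be called interim.
- *That the missing data monitoring committee (section 11.3.3) is part of the fault.* Such a committee would not normally govern the structure of an economic model.
- *That the threshold is a pass/fail test.* Section 6.5.2 gives a range and speaks of examining whether the ratio meets it.
- *That the conclusion is wholly unprotected.* The safeguards listed above are real, though incomplete.
- *That the chance of a falsely favourable ratio can be quantified.* Any such figure would need invented inputs. Alternative structures would also share the same trial effects, costs and utilities, so they could not be treated as independent.

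**Conclusion.** The concern holds in a limited form. Section 6.5.1 permits structural change informed by results, for a purpose expressed as presentation, while model type and horizon are open and without a duty to report the pre-change result. The comparison with £20,000 to £30,000 per QALY could therefore be influenced by results already seen.

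The size of any influence cannot be calculated from the protocol, and its direction is not established. The primary turnaround-time analysis is unaffected. The conclusion rests on reading the listed steps as being in time order and on the interim data actually entering the prototype; the wording supports both. It should be corrected, since the remedy is cheap and the sentence invites doubt about a stated secondary objective.

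**What to change.** In section 6.5.1:

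1. Delete the sentence about refining the value story.
2. State that the base-case structure and time horizon will be fixed in a dated specification before any prospective comparative result enters the model.
3. Allow later structural changes only for stated reasons of validity or new evidence, each logged with its date and rationale.
4. Require the result under the pre-specified base case to be reported beside the result under any revised structure.

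Interim data may still populate the prototype under these conditions, so early cost-effectiveness results need not be given up. The cost is a change of wording, a short specification and, if the structure changes, one extra reported model run.

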6.5.2 Objective

Compare costs and health benefits between pre and post implementation of qER and the associated ratios between the two to examine whether the ratio meets willingness to pay thresholds observed in England (i.e. £20,000 to £30,000 per QALY gained).

6.5.3 Health Economic Data

The data elements that will be used for the analysis of health economic assessment are listed below:

Intervention and comparator

- Numbers of ground truth positive and ground negative cases
- AI false positives, true positives, false negatives, true negatives

- AI output (+/- per disease)
- Radiologist output and/or agreement with AI decision per scan
- Time of admission to ED
- Time (with and without qER) of CT scan
- Time (with and without qER) time to ER physician viewing scan
- Time (with and without qER) to radiologist open scan
- Time (with and without qER) to radiologist report / close scan
- Time (with and without qER) ER physician opens report
- Time (with and without qER) to onwards referral
- Time (with and without qER) to treatment (need specific treatment per speciality pathway e.g. time to embolisation, time to surgery etc)
- Time to AI output delivered to PACS

Resource Use

- Number of head CTs performed out of hours
- Number of head CTs performed in hours
- Definition of in and out of hours per trust
- Reason for the scan (primary suspected diagnosis and/or main symptom)
- Death
- Reattendance to hospital with same presentation
- Transfer to other hospital
- Admission to same hospital, including care pathway
- Clinical diagnosis, including sub-type and severity of (e.g ASPECTS score for stroke, any relevant head trauma scales)
- False negative outcomes (e.g. missed diagnoses and severity)
- False positive outcomes (e.g. misdiagnosis and severity)
- Length of stay and wait in the ED
- Length of stay in hospital / wait to transfer

Costs

- AI implementation, maintenance, training, per scan costs
- Treatment cost per pathway/speciality (to be sourced from published literature)
- ED visit cost (to be sourced from published literature)
- Cost of hospital admission (to be sourced from published literature)
- Cost of hospital transfer (to be sourced from published literature)
- Cost by ward type (to be sourced from published literature)
- Cost of outsourcing CT head reading in and out of hours (to be sourced from published literature)

Utilities

- Will be applied to patient outcomes (values to be sourced from published literature)

6.6 Ground Truth

Both the prospective (stepped wedge) and retrospective (technical evaluation) elements of this study compare the performance of qER against ground truth and

ground truthing is required for confirming which scans contain a prioritised finding and not.

The following **prospective** scenarios (i.e. from the stepped-wedge study) will require independent generation of ground truth by two post-fellowship radiologists (and an arbitrating senior radiologist, where there is interobserver disagreement):

- All images where radiologist disagrees with the qER assessment.

Head-NCCT scans where original reporting radiologist agreed with Qer assessment will not be sent for ground truthing and the original report will be considered as the ground truth for such scans.

All NCCT head images will be reviewed by trust radiologist. Those that the trust radiologist disagrees will require independent generation of ground truth by two post-fellowship radiologists (and an arbitrating senior radiologist, where there is interobserver disagreement).

An image will be presented to ground truth radiologists only after the result has been generated by qER. Images from all sources will be presented in a single list for ground truth generation, so that radiologists cannot identify the source (i.e., whether the ground truth is necessary because there was a discrepancy, or not). All images will be deidentified to ensure the radiologist cannot identify the patient and thereby view the corresponding AI result or seek additional supporting clinical data to make a ground truth decision.

[figure not shown]

Figure 4: Ground truth for retrospective data.

[figure not shown]

Figure 5: Ground truth for prospective data.

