6.1.1.3 Post-Implementation

The implementation of new healthcare practices and the adoption of AI technologies is not linear. Study design and the elements of the study will enable evaluation of broadly the performance of the AI technology, acceptability, and the economic costs of adoption.

This randomised stepped wedge healthcare service delivery study to assess the clinical effectiveness of qER to prioritise patients reporting of NCCT scans that have prioritised findings (identified from AI analysis of a CT). The study will have an unaided (without qER

implemented) and aided phase (with qER implemented). During the unaided phase the reporting of CT will follow the same workflow as in the current standard of care (i.e., the images/cases will appear in the RIS chronologically and the radiologist either follows this order or prioritise some cases based on communication from ED). When the radiologist clicks a case in RIS, a secondary capture of qER along with the original images will be available in PACS.

During the post-implementation phase there will be a notification (prioritised flag) in RIS. The order of the cases in RIS will not be altered. When the radiologist clicks a case in RIS, a secondary capture of qER along with the original images will be available in PACS. This secondary capture will have contour showing the algorithm's attention point. The radiologist can choose to agree with qER findings as it or modify or ignore it according to their clinical judgement, writing and signing off the report. For scans which were not processed by qER the radiologist can prioritise and report as per the standard of care.

For the purposes of technical evaluation of qER, the scans taken during the aided phase will be divided into four categories:

- Scans with qER prioritised findings (prioritised pathway)
- Scans with qER non-prioritised findings (qER non-prioritised pathway)
- Scans not flagged as having no qER findings (qER no finding pathway), and
- Not interpreted (scans not processed by qER, Not interpreted pathway)

In the qER prioritised, qER non-prioritised and qER no finding pathway, all cases where the radiologist did not agree with qER findings will be sent for ground truthing (2+1 method, Figure 2). A random sample of 500 scans will also be sent for ground-truthing process for the purpose of technical evaluation.

[figure not shown]

Figure 2: Post-implementation workflow

[figure not shown]

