6.3 Secondary Outcome Measures

Utility of qER compared to standard of care:

- Time taken from acquisition to report NCCT head for patients without prioritised findings in Emergency Department
- Time taken from acquisition to report completed for patients with absence of findings on NCCT head scans in Emergency Department
- To assess impact of qER on radiology reporting workflow on other requests for CT scans
- To assess impact of teleradiology on qER supported reporting
- Time to diagnosis from CT acquisition.
- Time to referral from CT acquisition.
- Time to initiation of treatment from CT acquisition for prioritised scans.
- Death within 28 days of NCCT head acquisition
- Percentage of NCCT heads that qER classifies as prioritised and absence of findings.
- Percentage of qER non prioritised scans that radiologist identified as having prioritised finding
- Percentage of qER non prioritised but identified by radiologist as absence of finding.

Technical Evaluation of product performance:

- Sensitivity, specificity, positive and negative predictive values of qER in detecting scans with prioritized findings overall and also stratified by all 6 target abnormalities.
- Percentage of CT scans that could not be processed by qER due to technical factors.

Safety of qER:

- To assess the safety of qER of identifying patients with no prioritised findings identified on NCCT head.
- Percentage of patient NCCT Head reported incorrectly as qER non prioritised.
- Time from acquisition to reporting of CT Chest Abdo Pelvis (CAP) and Pulmonary Angiograms (CTPA) within the trust.

Health economic assessment:

- Compare costs and health benefits between pre and post implementation of qER, including cost evaluation of fully automatic diagnosis of high confidence normal triage.

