6.4 Technical Evaluation

The technical retrospective study will determine performance of the algorithm in each of the 4 sites. 500 NCCT scans will be identified for analysis from each site for technical evaluation. Sampling will be stratified by age, sex, month of year and target abnormalities.

The use of retrospective images and data has been approved by each site's Caldicott Guardian. In addition, approval for the release of anonymised patient data for research purposes forms part of the ethics application through IRAS.

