5.4.3 Post-scan

This record type will capture attributes that have occurred after the NHS radiologist final report was available for stakeholders to review including any patient follow-up data that is collected. For

attributes which are of 'binary' data types, a value of 1 will indicate the presence of that attribute and 0 indicates absence.

| | Attribute | Data type | Mandatory | Description | Source |
|---|--------------------|-----------|-----------|--|--------------------------|
| 1 | Patient identifier | Varchar | Yes | Unique identifies for a patient (across all sites) - likely to be conflation of site ID and site patient ID. | Assigned |
| 2 | SOP instance UID | Varchar | Yes | The unique ID for the image to which the report relates | DICOM Meta Data |
| 3 | Accession number | Varchar | Yes | Unique identifier linking the report to a suite of imaging studies | DICOM Meta Data |
| 4 | Rad ICH | Binary | Yes | Radiologist reported presence of Intracranial haemorrhage in the radiology report? | Clinical fellow's report |
| 5 | Rad MS | Binary | Yes | Radiologist reported presence midline shift in the radiology report? | Clinical fellow's report |
| 6 | Rad ME | Binary | Yes | Radiologist reported presence mass effect in the radiology report? | Clinical fellow's report |
| 7 | Rad Fracture | Binary | Yes | Radiologist reported presence cranial/skull fracture in the radiology report? | Clinical fellow's report |
| 8 | Rad Atrophy | Binary | Yes | Radiologist reported presence atrophy in the radiology report? | Clinical fellow's report |

| | | | | | |
|----|--|-------------------------------------|-----|--|--|
| 9 | Rad Infarct | Binary | Yes | Radiologist reported presence hypodensities suggestive of infarct in the radiology report? | Clinical fellow's report |
| 10 | Rad Other | Binary | Yes | Radiologist reported presence of any other findings other than the six target abnormalities in the radiology report? | Clinical fellow's report |
| 11 | Rad Scan Category | Integer | Yes | Prioritised or No Finding or Other non-prioritised finding? 1= Prioritised 2 = No finding 3 = Other non-prioritised finding | Derived from clinical fellow's report |
| 12 | Discordance between qER report and NHS Trust radiologist report | Binary | Yes | Is there a discordance between qER report findings and NHS Trust radiologist report? 1 = Yes 0 = No | Derived from clinical fellow's report and qER report |

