5.4.4 Ground truth

This record type will contain attributes that captures the ground truth results for the Head NCCT scans which have findings that are discordant between qER report and NHS trust radiologist report.

| | Attribute | Data type | Mandatory | Description | Source |
|---|--------------------|-----------|-----------|--|----------|
| 1 | Patient identifier | Varchar | Yes | Unique identifies for a patient (across all sites) - likely to be conflation of site ID and site patient ID. | Assigned |

| | | | | | |
|----|---------------------|---------|-----|--|---------------------|
| 2 | SOP instance UID | Varchar | Yes | The unique ID for the image to which the report relates | DICOM Meta Data |
| 3 | Accession number | Varchar | Yes | Unique identifier linking the report to a suite of imaging studies | DICOM Meta Data |
| 4 | Ground truther ID | Varchar | Yes | The unique ID of the person generating ground truth | Assigned |
| 5 | Ground truther role | Varchar | Yes | 'Adjudicator' if the ground truther is adjudicating a disagreement between two ground truthers, otherwise 'Default ground truther' | Assigned |
| 6 | GT ICH | Binary | Yes | Ground truther reported presence of intracranial haemorrhage in the radiology report? | Ground truth report |
| 7 | GT MS | Binary | Yes | Ground truther reported presence midline shift in the radiology report? | Ground truth report |
| 8 | GT ME | Binary | Yes | Ground truther reported presence mass effect in the radiology report? | Ground truth report |
| 9 | GT Fracture | Binary | Yes | Ground truther reported presence cranial/skull fracture in the radiology report? | Ground truth report |
| 10 | GT Atrophy | Binary | Yes | Ground truther reported presence atrophy in the radiology report? | Ground truth report |

| | | | | | |
|----|------------------|---------|-----|--|----------------------------------|
| 11 | GT Infarct | Binary | Yes | Ground truther reported presence hypodensities suggestive of infarct in the radiology report? | Ground truth report |
| 12 | GT Other | Binary | Yes | Ground truther reported presence of any other findings other than the six target abnormalities in the radiology report? | Ground truth report |
| 13 | GT Scan Category | Integer | Yes | Prioritised or No Finding or Other non-prioritised finding? 1= Prioritised 2 = No finding 3 = Other non-prioritised finding | Derived from ground truth report |

APPENDIX 6

GP Letter

qER Evaluation

GP LETTER

Qure.AI qER

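### Section 6.6 keeps agreed prospective scans from the panel and takes the qER-aided report as truth; this must be reconciled with the random 500 of 6.1.1.3 and leaves shared errors scored as correct

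*Protocol*

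**What the plan says.** Section 6.6 sets the ground-truth rule for both parts of the study. From the stepped-wedge part, the only group it lists for independent reading is scans where the radiologist disagrees with qER. For the others, "Head-NCCT scans where original reporting radiologist agreed with Qer assessment will not be sent for ground truthing", and their original report stands as the truth. In the aided phase that report is not independent of qER. Section 6.1.1.3 puts the qER capture in PACS beside the images when the case is opened, and adds: "The radiologist can choose to agree with qER findings as it or modify or ignore it according to their clinical judgement".

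Section 6.1.1.3, where it divides aided-phase scans into categories, sends all disagreements to ground truthing and then says: "A random sample of 500 scans will also be sent for ground-truthing process for the purpose of technical evaluation". Section 6.4, on the retrospective part, gives a different number: "500 NCCT scans will be identified for analysis from each site for technical evaluation", with stratified sampling.

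Three other places bear on the point:
- Appendix 5, section 5.4.4, describes a ground-truth record that "captures the ground truth results for the Head NCCT scans which have findings that are discordant between qER report and NHS trust radiologist report".
- Appendix 5, section 5.4.3, defines the discordance field by asking: "Is there a discordance between qER report findings and NHS Trust radiologist report".
- Section 6.6 puts all images in a single list so that the readers cannot tell "whether the ground truth is necessary because there was a discrepancy, or not".

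The outcomes in section 6.3 that need a truth label include sensitivity, specificity and predictive values for prioritised findings and, under safety, "Percentage of patient NCCT Head reported incorrectly as qER non prioritised".

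**The concern.** There are two linked problems. First, 6.6 and 6.1.1.3 give different instructions for the same scans. A random draw from the aided phase would consist mostly of scans on which the radiologist agreed with qER, and 6.6 bars those from the panel. Whichever section a site follows decides whether the truth for these scans is a panel reading or the original report.

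Second, if 6.6 is followed, agreement is treated as correctness. The safety outcome asks how often qER wrongly fails to prioritise a scan. The miss that matters most for that question is the one the radiologist also makes with the qER output in view. On a scan with no other discordant finding, nobody re-reads it, and it enters the tables as a correct negative. A false flag that the radiologist accepts enters as a true positive. Section 6.5.3 also lists the AI true and false positives and negatives as inputs to the economic model, so the labels carry further than the accuracy table.

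**Working it through.** **The plan's own figure.** Section 15.1 has 35 abnormal scans per site per month: 35 × 4 sites × 12 months = 1,680. At about 10% abnormal, 1,680 / 0.10 = 16,800 scans. Both figures reproduce. Only the 10% is used below, taken as the prevalence of prioritised findings.

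**Assumed inputs (not in the protocol).** qER sensitivity 90% and specificity 90%; *j* = share of qER misses that the radiologist also misses; *a* = share of qER false flags that the radiologist accepts. The panel is taken as correct on discordant scans, and the safety percentage as the share of scans not prioritised by qER that do have a prioritised finding.

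**Per 1,000 scans, true counts:** TP 90, FN 10, FP 90, TN 810.

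**Counts under 6.6:** TP′ = TP + a·FP; FN′ = FN(1 − j); FP′ = FP(1 − a); TN′ = TN + j·FN. TP′ and TN′ can only grow, and FN′ and FP′ can only shrink. Sensitivity, specificity, PPV and NPV can therefore only stay equal or rise.

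**Shared misses (a = 0).** The true values are sensitivity 90% and wrongly classed 10/820 = 1.22%.

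| j | Apparent sensitivity | Apparent share wrongly classed |
|---|---|---|
| 2% | 90/99.8 = 90.2% | 9.8/820 = 1.20% |
| 10% | 90/99 = 90.9% | 9/820 = 1.10% |
| 40% | 90/96 = 93.75% | 6/820 = 0.73% |

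**If half of the shared misses reach the panel** because another finding on the scan is discordant, FN′ = 10(1 − j/2). Apparent sensitivity is then 90/99.9 = 90.1%, 90/99.5 = 90.5% and 90/98 = 91.8%.

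**Accepted false flags (j = 0).** PPV = (90 + 90a)/180, which moves from 50% to 51% at a = 2% and 55% at a = 10%. Specificity = 810/(810 + 90(1 − a)), which moves from 90% to 90.2% and 90.9%.

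**Panel error, at j = 10%.** Suppose radiologists overcall 2% of the 810 true negatives (16.2 scans) and the panel wrongly upholds some of these.
- 5% upheld adds 0.81 false misses: 90/99.81 = 90.2%.
- 10% upheld adds 1.62: 90/100.62 = 89.4%, below the true 90%.

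**What a random 500 would contain, at j = 10% and a = 0.**
- Agreed scans: 90 + 810 + 1 = 901 per 1,000, so about 450 of 500.
- Agreed and not prioritised by qER: 811 per 1,000, so about 405 of 500.
- Expected shared misses: 500 × 0.010 × j = 0.1, 0.5 and 2.0 at j = 2%, 10% and 40%.
- If none is found in 405, the one-sided 95% upper bound is 1 − 0.05^(1/405) = 0.74%. That is 0.0074 × 811 = 6.0 hidden misses per 1,000, so sensitivity could be as low as 90/(99 + 6.0) = 86%.
- If one is found in 405, that is 811/405 = 2.0 per 1,000, and the estimate becomes 90/101.0 = 89.1%, against an apparent 90.9%.

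**The case against.** The strongest reply is that there may be no contradiction. Section 6.1.1.3 does not state the sampling frame of the 500. Section 6.6 links technical evaluation with the retrospective part, and 6.4 uses 500 for the same purpose. The 500 could be a loose reference to that sample. This cannot be excluded, and Figures 2 and 5, which may show where the 500 enter, are not visible. But the sentence stands in a paragraph on aided-phase scans, which are themselves divided there for technical evaluation. It describes one random 500, not a stratified 500 per site. If the retrospective reading is right, no agreed prospective scan is due for the panel and three sections still need reconciling.

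Other points stand in part:
- The discordance field compares report findings. If disagreement on any of the six findings sends a scan to the panel, some shared misses will surface there.
- The single reading list implies that it holds some non-discrepant images. These may be the retrospective ones, and this does not lift the explicit bar.
- Section 5.4.4 is weak support. Read literally it would also omit the retrospective panel reads, so it is probably just incomplete.
- Reading only discordant scans is a reasonable economy with 16,800 expected. That justifies not reading every scan; it does not make unverified agreement a reference standard.
- The form of a weighted analysis may be left to the SAP. Which scans are verified, and what counts as truth, is fixed here in the protocol.

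A reader might infer that the trial's accuracy results are shown to be inflated, or materially so. The documents do not support that. They give no accuracy, shared-miss, overcall or panel-error rate; the direction depends on an accurate panel, and modest panel error can cancel or reverse it. Nor do they show that the retrospective sensitivity, specificity and AUC of section 6.4 are affected.

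**Conclusion.** The concern holds for the prospective figures. On the plain reading, 6.6 and 6.1.1.3 give incompatible instructions for agreed aided-phase scans. Under 6.6 as written, errors shared by qER and the aided radiologist on unverified scans are scored as correct. Given an accurate panel, prospective sensitivity, specificity, PPV, NPV and the safety percentage then equal the truth or favour qER.

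The size is unknown and may be small. At shared-miss rates of 2% to 10% the gain in sensitivity is 0.2 to 0.9 points; only at a high rate such as 40% does it approach 4 points. These figures rest on the assumed 90% sensitivity and specificity, and on no shared miss reaching the panel through another finding. The point merits correction because the safety outcome is the one least able to rest on unverified agreement, and the reads needed appear to be planned already.

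**What to change.** Amend 6.6, and align Appendix 5.4.4, so that the random 500 of 6.1.1.3 goes to the panel whether or not the radiologist agreed with qER, with the panel result as truth. State that it is a simple random sample of qER-processed aided-phase scans. Use its agreed scans, weighted up to all agreed scans, together with the fully read discordant scans at weight one, for a verification-corrected estimate of prospective accuracy and of the safety percentage, with its interval. Label any figure that takes the original report as truth as agreement-based.

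If the 500 is in fact the retrospective sample of 6.4, say so, correct the number, and label the prospective accuracy and safety figures as agreement-based.

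The cost is wording in three places and a weighted analysis. No panel reads are added beyond those planned, provided that the 500 is separate from 6.4. The drawback is precision: with about 405 agreed scans not prioritised by qER, roughly 0.1 to 2 shared misses are expected, and finding none would still allow a sensitivity of about 86%. The corrected interval will be wide, and should be reported as such.
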